3.1 General Design

This is a long-term longitudinal observational case-control study. Basic blood tests to include measuring renal function, haemoglobin, albumin and proteinuria will be measured at study entry as well as 1 year, 3 years, 5 years and 10 years after AKI (approximately 9months, 33months, 57 months and 117 months after recruitment). Samples will also be collected and stored at each of these time points for subsequent biomarker measurement; these will consist of inflammatory markers (IL-6, high sensitivity CRP) and plus a panel of biomarkers of tubular injury (to include NGAL and IL-18). Included patients will have baseline demographics, co-morbidity and acute illness details extracted from the hospital PAS system. AKI stage and baseline renal function (that prior to sustaining AKI) will be extracted from the electronic AKI reporting system currently in clinical use at the Royal Derby Hospital. This novel system identifies all episodes of AKI from every inpatient location and also reports severity as per AKIN staging; the diagnostic accuracy of this system has been confirmed and reported previously [16].

Patients receiving acute dialysis during the episode of AKI will be identified from renal unit and intensive care unit databases; the renal database (Vitaldata) will be used to identify those patients who subsequently require chronic renal replacement therapy (RRT). The Medical Research Information

Service (MRIS, an arm of the NHS Information Centre) will be used to accurately track survival data of participants to **ten** years after the AKI episode.

A pilot study, specifically designed to test this methodology and recruitment process is currently underway, and demonstrates that the proposed recruitment, consent and matching processes are both practicable and feasible (recruitment rate ~20%, with approximately 15 participants recruited per week).

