4.3.2 Data Collection and Follow-up for Withdrawn Subjects

Patients who withdraw will be asked to allow data collected prior to the date of withdrawal to be retained for analysis. They will also be asked to allow outcome data, including clinical events and the

results of any kidney function tests arranged by the GP, to be collected for future analysis. If a participant declines this their data will be deleted.

Patients who fail to attend for blood tests will be contacted by telephone to determine whether or not they are willing to continue. Patients without access to a telephone will be contacted by letter. If no response is received to two letters sent one month apart, the patient will be assumed to have been lost to follow-up.

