8.3 Subject Population(s) for Analysis

All patients will be included in the analyses described above except for those in the control group who subsequently sustain AKI during the study period, who will be excluded. Depending on the frequency of this occurrence a separate 'intention to treat' secondary analysis may be performed. Data from patients who withdraw (and give consent) or who die will be included until the date of withdrawal or death.

9 Safety and Adverse Events

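### Section 8.3 stops using withdrawn patients' data at withdrawal, although section 4.3.2 seeks permission to collect and analyse their later outcomes

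*Protocol*

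**What the plan says.** Section 4.3.2 of the protocol makes two separate requests of a patient who withdraws consent. The first concerns the past: "Patients who withdraw will be asked to allow data collected prior to the date of withdrawal to be retained for analysis". The second concerns the future: "They will also be asked to allow outcome data, including clinical events". This second request extends to GP-ordered kidney tests, and its stated purpose is later analysis. The section then adds: "If a participant declines this their data will be deleted".

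Section 8.3 sets the rule for the analysis: "Data from patients who withdraw (and give consent) or who die will be included until the date of withdrawal or death". The analyses it governs are those of section 8.2, namely Kaplan-Meier curves with the log-rank test and an adjusted Cox model for the two primary endpoints. Section 3.2 gives these as death and CKD progression, the latter including the start of renal replacement therapy (RRT).

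Two sources of outcome data need no study visit. Under section 3.1 the Medical Research Information Service (MRIS) "will be used to accurately track survival data of participants" up to ten years after the AKI episode, and the renal database identifies patients who later need chronic RRT.

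Patients who miss blood tests are treated separately. If they cannot be reached, section 4.3.2 says that "the patient will be assumed to have been lost to follow-up".

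**The concern.** The two sections give different rules for the same people. One asks them for permission to collect later outcomes so that these can be analysed. The other stops their contribution on the day they withdraw, even where they have agreed. No other analysis in the protocol would use the later data.

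Both primary endpoints are affected, because the permission covers clinical events and kidney function results. Leaving these out loses events in a study that expects few renal ones. It also makes the Kaplan-Meier and Cox results depend on withdrawal being unrelated to outcome given the covariates, where permitted data could have reduced that dependence. There is a further matter of good faith: patients would be asked for data that the analysis rule then sets aside.

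**Working it through.** **Comparing the sections**

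- Who is withdrawn: under section 4.3, only patients who withdraw consent. The cut-off in 8.3 therefore applies to them and not to non-attenders.
- What may be collected afterwards: under 4.3.2, clinical events and GP kidney results, if the patient agrees.
- What may be analysed: under 8.3, nothing after the withdrawal date. The words in brackets in 8.3 could refer to either permission in 4.3.2, but on both readings the inclusion ends at withdrawal.
- Whether record linkage continues: not stated. Passing identifiers to MRIS rests on consent (4.2.2 and 4.2.3), and 4.3.1 removes withdrawn patients at once.

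The contradiction lies in the text. The protocol gives no figure for its effect, so there is none to reproduce. The illustrations below use the planning rates together with labelled assumptions.

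**Expected renal events.** Inputs from section 8.1: 542 patients per group, and 2.02% (control) and 4.41% (AKI) progressing. With everyone fully followed:

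542 × (0.0202 + 0.0441) = 542 × 0.0643 = 34.9, about 35 events.

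**Events lost by stopping at withdrawal.** Assume that a fraction *w* withdraws at mid-follow-up, that all of them would have permitted later data, and that their risk is unchanged afterwards. About half of their events then fall after withdrawal:

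lost events ≈ 34.85 × *w*/2

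- *w* = 5%: 34.85 × 0.025 = 0.9
- *w* = 10%: 34.85 × 0.05 = 1.7
- *w* = 26%: 34.85 × 0.13 = 4.5

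The top of the range treats the whole drop-out allowance of section 8.1 as consent withdrawal, so it is an upper end and not an estimate. The protocol gives no planning death rate, so no similar count is possible for mortality.

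**Possible bias.** Let *p* be a group's planning risk, *h* = −ln(1 − *p*) its cumulative hazard, and *k* the factor by which the hazard changes after withdrawal at mid-follow-up.

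- Risk when later events are counted: (1 − *w*)(1 − e^(−*h*)) + *w*(1 − e^(−*h*(0.5 + 0.5*k*)))
- Risk estimated when withdrawn patients are censored: 1 − e^(−*h*) = *p*, so the observed ratio is 0.0441/0.0202 = 2.18 throughout

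Worked example with *k* = 3 and *w* = 26% in both groups:

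- Control: 0.74 × 0.0202 + 0.26 × (1 − 0.9798²) = 0.0149 + 0.0104 = 0.0253
- AKI: 0.74 × 0.0441 + 0.26 × (1 − 0.9559²) = 0.0326 + 0.0224 = 0.0551
- True ratio 2.17, against 2.18 observed

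| Assumed withdrawal (control / AKI) | *k* | True ratio | Observed ratio |
|---|---|---|---|
| any of those tried | 1 | 2.18 | 2.18 |
| 10% / 10% | 1.5 to 3 | 2.18 | 2.18 |
| 26% / 26% | 1.5 to 3 | 2.18 to 2.17 | 2.18 |
| 20% / 32% | 1.5 to 3 | 2.24 to 2.38 | 2.18 |

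With equal withdrawal the ratio hardly moves, but the absolute risks are understated: at *k* = 3 and 26% the true risks are 2.5% and 5.5%, against 2.0% and 4.4% estimated. The ratio shifts visibly only when risk rises after withdrawal and withdrawal also differs between groups.

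**The case against.** The strongest reply is that this is a small wording mismatch affecting an unknown and perhaps small subset, and that stronger conclusions are not supported. Much of that stands. Four inferences that a reader might draw should be set aside.

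- *Non-attenders are also cut off, so deaths and RRT are lost at a missed blood test.* No section says so. Section 4.3 confines withdrawal to withdrawal of consent, 4.3.2 handles non-attenders separately, and 3.1 does not make MRIS or renal-database tracking depend on attendance. A clarifying sentence is useful, but there is no stated rule to correct.
- *The 26% drop-out measures the damage.* That would be 0.26 × 542 = 141 patients per group. But the 26% is all drop-out, the share due to consent withdrawal is not given, and withdrawn patients still contribute follow-up until they leave. Precision in a log-rank or Cox analysis depends mainly on events, not on head-count.
- *Censoring is informative and both primary endpoints are biased.* The protocol does not link withdrawal to prognosis. This is plausible in patients recovering from acute illness, but it is not shown.
- *The study already holds the later deaths.* Under 4.3.2 patients are asked, so they may refuse, and the protocol does not say that consent to linkage survives withdrawal.

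It could also be said that censoring detail belongs in a statistical analysis plan. That would answer an omission. Here the protocol states a rule that conflicts with another of its own sections, and an analysis plan that follows 8.3 would inherit the conflict.

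**Conclusion.** The point holds in a limited form. For patients who withdraw consent but permit later outcome data, 8.3 excludes from both primary analyses what 4.3.2 sets out to collect for analysis, and the two sections must be reconciled.

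The size cannot be determined from the protocol. The illustrated loss of renal events assumes withdrawal at mid-follow-up, unchanged risk afterwards, full permission and the planning rates. It shrinks in proportion if fewer patients withdraw or some refuse permission. Informative censoring is a possibility to guard against and not a demonstrated bias. Ending follow-up at death is normal and is not criticised.

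**What to change.** Amend section 8.3 to follow the permissions sought in 4.3.2:

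- **Later outcome data permitted:** the patient stays in the primary analyses after withdrawal. Deaths and RRT are counted where the permission covers record linkage. Creatinine-based endpoints are followed to the last permitted result, including GP tests.
- **Only earlier data may be kept:** the patient is censored at the date of withdrawal.
- **Non-attendance:** state, for clarity, that missing blood tests alone does not end follow-up for death through MRIS or for RRT through the renal database.

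The deletion sentence in 4.3.2 should also say which refusal triggers it, so that a patient who refuses later data but allows earlier data to be kept clearly falls in the second category.

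The cost is about one paragraph in 8.3, and the data sources are already in the protocol. The small downside is that the consent or withdrawal wording may have to state that the permission covers record linkage, which may need ethics approval. Continued linkage should not become the default for withdrawn patients, because 4.3.2 makes later data a matter of agreement.

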9.1 Recording of Adverse Events

All Adverse Events (AE) Serious Adverse Events (SAE) will be recorded according to the R&D Office Procedure and the Trust Policy on Incident Reporting.

9.2 When Adverse Events are Recorded

As this is an observational study with no study procedures other than venesection it is not anticipated that there will be any adverse events directly related to the study and no adverse event data for non-serious adverse events will be collected.

Despite this, it is important that this protocol includes a process for dealing with any unexpected serious adverse events in the unlikely event they occur. Serious adverse events that are considered expected in the investigator's judgement will be captured on a SAE log. If a trial subject experiences a serious adverse event which in the opinion of the chief investigator is both related (resulted from administration of any of the research treatments or procedures) and unexpected then it will be reported to the Research Ethics Committee that gave a favourable opinion of the study and the sponsor DHFT within 15 days of the Chief Investigator becoming aware of the event using the NRES safety report form available from:

http://www.nres.nhs.uk/applications/after-ethical-review/safetyreports/safety-reports-for-all-other-research/

If the event fulfils the requirement of an IR1, it will also be reported according to Trust Policy. The clinical course of each SAE will be followed until resolution, stabilization, or until it has been determined that the study participation is not the cause. Serious adverse events that are still ongoing at the end of the study period will be followed up to determine the final outcome.

10 Data Handling and Record Keeping

10.1 Confidentiality

Information about study subjects will be kept confidential and managed according to the requirements of the Data Protection Act, NHS Calldicott Guardian, The Research Governance Framework for Health and Social Care, Ethics Committee Approval and Trust IM&T Policy. Any information given as required for participant health status tracking to MRIS will be delivered in encrypted form.

Patient contact details including name, address and telephone number will be collected. This information will be retained to facilitate contacting the participants to arrange follow-up tests. Only the research team will have access to this database. It will be stored on a Trust password-protected server. A single hard copy will be stored in a locked filing cabinet in the data custodian's office.

Each participant will be assigned a unique study number. The patient's name, date of birth and study number will be stored in a single password protected file on a Trust server. Only the research team will have access to this file. All data collected for the study will be entered into a separate database in which data will be labelled only with the study number. The participant's hospital number will be entered into this database but without any other identifiable details. Participants will not be identifiable from any publications arising from this study.

The Trust has a comprehensive registration with the Information Commissioner with research being registered under Purpose 4 of the Register; The Trust Data Protection Officer will be notified of all research studies in order to comply with the Trust IM&T Security Policy.

[name] will act as "Custodian" of the data.

10.2 Source Documents

Source documents for this study will include:

- Case report form (results section)
- Laboratory results reports

10.3 Case Report Forms

Each participant will have a data collection form covering all study results, labelled with the unique study number. These will be completed in accordance with the principles of Good Clinical Practice.

10.4 Records Retention

All paper records will be stored in a locked filing cabinet within the Trust or Medical School for the duration of the study. Computer records will be stored in password-protected files on password-protected servers in the Trust. At the conclusion of the study all data will be archived and stored for 5 years in a secure storage facility in accordance with Trust policy.

Three copies of the consent from will be obtained. One will be retained by the participant and the others will be filed in the participant's hospital records and with the data collection form (in the TMF) respectively.

11 Study Monitoring, Auditing, and Inspecting

11.1 Study Monitoring Plan

The investigator will permit study-related monitoring, audits and inspections by the Ethics Committee, the Sponsor and the Research Governance Manager. This study will be monitored by the Research Governance Manager according to the Research & Development Office procedure for monitoring all non-commercial research carried out at the Derby Hospitals NHS Foundation Trust. In line with the responsibilities set out in the Research Governance Framework, the Investigator will ensure that the research governance manager or other regulatory monitoring authority is given access to all study-related documents and study related facilities.

12 Ethical Considerations

This study will be conducted according to the standards of International Conference on Harmonisation, Good Clinical Practice Guideline, Research Ethics Committee regulations, any applicable government regulations, Trust and Research Office policies and procedures.

This protocol and any amendments will be submitted to a properly constituted Research Ethics Committee (REC) for approval of the study conduct. The protocol will also be submitted to the National Information Governance Board for specific approval of the participant screening process.

All subjects for this study will be provided with an information sheet describing the elements of this study and sufficient information for subjects to make an informed decision about their participation in this study. See Attachments for a copy of the Information Sheet. The subject will complete and sign a consent form to indicate that they have given valid consent to participate.

As this is an observational study it is not anticipated that any ethical problems will arise. Children and vulnerable adults will not be included.

13 Study Finances

13.1 Funding Source

It should be noted that the anticipated costs of this project are low due to the straightforward protocol and local funds are already in place to allow project start-up. Funding has been secured in the form of a Research Grant from the BUPA Foundation.

13.2 Indemnity for the performance of the study

NHS indemnity will apply in the event of a claim by, or on behalf of, participants for negligent harm. There will be no special arrangements for non-negligent harm but the normal NHS Complaints mechanism will be available to all participants.

